2.1. Synopsis of study protocol

The primary objective of this randomized controlled trial is to examine the impact of a behavioral support intervention for adults with type 1 diabetes (T1D) who are starting on continuous glucose monitoring (CGM). This trial compares adults with T1D who are starting on CGM with behavioral supports (the intervention group) versus those who are starting on CGM without behavioral supports (the control group). We will examine group differences over a 3-month period on two sets of outcomes. The first set of outcomes includes glycemic variables (e.g. hemoglobin A1c, time in range). In this set of outcomes, A1c is the identified primary endpoint. The second set of outcomes includes psychosocial variables (e.g. diabetes distress, worry about hypoglycemia, technology attitudes), with diabetes distress as the primary endpoint. After the initial comparison of intervention to control across the first 3 months after starting CGM, we will conduct a longitudinal follow-up of glycemic and psychosocial outcomes at 6 and 12 months.

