2.7. Data analysis plan

Our team has extensive experience in the use of web-based assessment, data management and data analysis. Quantitative data will be entered into an online encrypted, HIPAA-compliant data management system, REDCap, with secure access for unique study IDs assigned to each participant. REDCap survey data is then ready for download by study staff and will be imported into SPSS for data cleaning and analysis. CGM data will be downloaded via Dexcom Clarity and LibreView which create a CSV file for transfer to REDCap and data analysis programs.

Demographic, medical, psychosocial variables, and some outcome measures are surveys and multi-item scales that participants will answer in REDCap. Psychometric properties of scales will be assessed before proceeding to investigate the proposed aims. These psychometric properties include item-total correlations and Cronbach's α to assess reliability. Total scores and subscale scores, when available, will be calculated and used for statistical analyses. Descriptive statistics will calculate frequencies, means and standard deviations for study variables. Independent samples t-tests and χ^2 analyses will assess potential differences between groups at baseline in demographic, psychosocial and diabetes variables. Analyses for Hypotheses 1&2 will follow the intention-to-treat principle.

To test Hypotheses 1&2, we will first conduct a treatment group comparison (ONBOARD vs. CGM-only) of the change in A1c, the primary outcome, from baseline to 3, 6, and 12 months. Specifically, we will use linear mixed models to model changes in A1c as a function of time, intervention assignment, and group-by-time interaction. These models will include a subject-specific random effect to account for the correlation of

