outcomes over time within a subject. We will examine change from baseline for each outcome as the dependent variable. We will begin by fitting models with minimum covariates prior to considering additional covariates. Similar models will be used to examine secondary outcomes of time in range, days of CGM wear (Hypothesis 1), diabetes distress, and perceived CGM benefit (Hypothesis 2). We will reference information criteria (e.g., Akaike's) to inform model selection decisions. Beyond testing the groups-by-time interaction term, custom contrasts will assess group differences at each time point. Exploratory analyses will examine differences between subgroups over time after primary, intent-to-treat analyses are completed. Additional exploratory analyses will examine patient-level predictors of CGM wear (e.g. age, gender, diabetes duration). For the CGM-continuer subgroup, we will conduct exploratory longitudinal analyses using CGM data to look at changes in time in range. We will adjust for multiple comparisons by using the Benjamini-Hochberg procedure and a false discovery rate of 0.05 (78). Analyses will initially be conducted without imputation for missing values, using the missing-at-random approach (79) and then multiple imputation will be used to supply values for missing data. We will conduct sensitivity analysis by multiple imputation to compare the effects.

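### Diabetes distress is a primary endpoint in 1.1 and 2.1 but secondary in 2.7, and the Benjamini-Hochberg family is undefined, so the level for A1c and the standing of a distress claim cannot be determined from the plan

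*Combined protocol and SAP*

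**What the plan says.** Sections 1.1 and 2.1 carry the same text. They describe two sets of outcomes: "We will examine group differences over a 3-month period on two sets of outcomes". For the glycemic set, "In this set of outcomes, A1c is the identified primary endpoint"; the psychosocial set is introduced "with diabetes distress as the primary endpoint". That makes two primary endpoints. Months 6 and 12 are described as longitudinal follow-up.

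Section 2.7 begins with a group comparison "of the change in A1c, the primary outcome, from baseline to 3, 6, and 12 months", with one primary outcome and three time points. Similar models are then planned for the secondary outcomes: time in range and CGM wear under Hypothesis 1, and "diabetes distress, and perceived CGM benefit (Hypothesis 2". For each outcome the plan tests the group-by-time interaction and a group contrast at each visit; exploratory subgroup and predictor analyses follow. On multiplicity it says: "We will adjust for multiple comparisons by using the Benjamini-Hochberg procedure and a false discovery rate of 0.05 (78". No family is listed, and A1c is neither placed in it nor exempted.

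The sample-size paragraph of 2.7 powers A1c only, at alpha .05. It gives no power for distress and no split or ordering of alpha between the two endpoints.

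**The concern.** These are current passages in conflict, and nothing says which section prevails. The consequence is easiest to see in an example. Suppose A1c is not significant and distress has p = .03.

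- Under 1.1 and 2.1, with each primary tested at .05, this is a success on a primary endpoint.
- Under 1.1 and 2.1, with Benjamini-Hochberg on the two primaries, distress needs p ≤ .025 when A1c exceeds .05, so it fails.
- Under 2.7 it is a secondary finding. Whether it survives adjustment depends on which tests are counted and on their p-values. With all five named outcomes in the family and the other four clearly null, it would need p ≤ .01.

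The same data can thus support different headline conclusions, and the choice could be made after the p-values are known. The level for A1c is also open: .05 if it stands outside the family, and between .05/m and .05 if it is one of m tests in it.

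**Working it through.** **Inputs from 2.7:** 89 per arm randomised; 76 per arm after 15% attrition; d = .35; alpha .05; autocorrelation .50; repeated measures on change to 3, 6 and 12 months. **Assumed:** two-sided alpha, equal correlation between visits, and independent tests.

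**1. Reproduce the stated power.** In units of the single-visit SD, the mean of three follow-ups has variance (1 + 2×.5)/3 = .667, so SD .816. Subtracting baseline gives .667 + 1 − 2×.5 = .667, the same. The noncentrality is (.35/.816)×√(89/2) = 2.86. Two-sided power at .05 is .816 (normal) or .812 (noncentral t), which agrees with the plan's claim to exceed 0.80. With 76 per arm the noncentrality is 2.64 and power is .753 or .747.

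**2. Error rate with two primaries.**
- Each at .05, unadjusted, both null, independent: 1 − .95² = .0975.
- Benjamini-Hochberg on exactly those two rejects both if both p ≤ .05, and otherwise rejects the smaller if it is ≤ .025. This is Hochberg's procedure. Error with both null: .05² + 2×.025×.95 = .0025 + .0475 = .05.
- Benjamini-Hochberg on the five outcomes named in 2.7 controls the false discovery rate, not the family-wise rate. In simulation the chance of any false rejection reached about .088 (two real effects, three null). The chance of a false claim on A1c or distress was about .079 when the other three effects were real.

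**3. Power for A1c if it is inside the family.** For two tests, with P(α) the power at level α, power is P(.025) + [P(.05) − P(.025)] × Pr(distress p ≤ .05). By the noncentral t at 89 per arm:
- distress null: .725 + (.812 − .725)×.05 = .729;
- distress with the same effect: .725 + (.812 − .725)×.812 = .795 (inputs unrounded).

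The five-test figures come from simulation with 400,000 runs. Each cell gives normal / t.

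| How A1c is tested | 89 per arm | 76 per arm |
|---|---|---|
| .05, outside the family | .816 / .812 | .753 / .747 |
| Family of 2, other null | .736 / .729 | .661 / .653 |
| Family of 2, other has same effect | .800 / .795 | .729 / .722 |
| Family of 5, others null | .618 / .609 | .534 / .522 |
| Family of 5, others have same effect | .791 / .785 | .712 / .704 |
| Fixed .025 | .732 / .725 | .656 / .648 |

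**4. If the primary test is the single 3-month comparison.** The variance of change is 1 + 1 − 2×.5 = 1. At .05, power is .646 / .641 with 89 per arm and .578 / .573 with 76. This shortfall comes from the choice of time point, not from multiplicity.

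**The case against.** Section 2.7, read alone, is coherent: A1c is the single primary outcome, it is tested first, it alone is powered at .05, and the adjustment can be taken to cover the rest. On that reading the A1c level is exactly the one used for power. This is the most natural reading of 2.7, and it limits the point in three ways.

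- A reader might infer that A1c will be tested at something other than .05. The documents do not support that, because they never place A1c in the family. What stands is that they never exempt it either.
- A reader might infer that the trial runs at 9.75% family-wise error. That requires both endpoints to be primary and both to escape the adjustment. If Benjamini-Hochberg covers exactly those two, the error is 5%.
- A reader might infer a severe loss of power for A1c. The larger losses need every other outcome to be null, whereas the trial hypothesises benefit on them. If they share the effect, the loss at 89 per arm is one to three percentage points.

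The contradiction over distress survives all of this. The natural reading of 2.7 does not cancel the statement, made in both 1.1 and 2.1, that distress is a primary endpoint.

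**Conclusion.** The point holds as an inconsistency and an undefined rule, not as a demonstrated error in the A1c test. Distress has two incompatible statuses, and the level for A1c cannot be read from the plan. The family-wise error for the two endpoints lies anywhere from 5% (controlled together) to 9.75% (unadjusted, independent) if both are primary. A1c power at 89 per arm is about .81 if A1c is outside the family. Inside it, power is about .73 (two tests) or .62 (five) with the other outcomes null, and about .80 or .79 with the same effect on all. These figures rest on the assumptions listed above. In particular, the powered contrast is inferred to be the mean over three follow-ups because that formula reproduces the plan's figure. Correlated outcomes would change the simulated values somewhat. The matter should be settled before any unblinded comparison of outcomes.

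**What to change.** 1. Give distress one status in 1.1, 2.1 and 2.7.
2. The option that keeps the powered level: A1c is the sole primary, tested at two-sided .05 on the contrast that was powered, and declared outside Benjamini-Hochberg. Distress is secondary, for example a key secondary tested at .05 only if A1c is significant. Benjamini-Hochberg at 0.05 then applies to a listed set of the remaining secondary outcomes and contrasts.
3. If both are to stay primary, control them together (.025 each, or Hochberg) and restate A1c power: at .025, about .73 with 89 per arm and .65 with 76. Give power for distress as well.
4. Name the primary contrast or time point, since 1.1 and 2.1 point to 3 months and 2.7 to all three visits. If it is the single 3-month comparison, restate power at about .64 with 89 per arm and .57 with 76.

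Which status distress should have is the sponsor's choice; the plan needs to make it once.

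Cost: option 2 changes wording only, with no new data or visits, but under the key-secondary example a formal distress claim depends on the A1c result. Two primaries, or a 3-month primary test, also require a restated and less favourable power figure.

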2.2. Study procedures

Participants will be recruited at Stanford University through a combination of in-clinic, in community locations and online through type 1 diabetes online communities. Eligible participants will be adults (ages 18-50) who have not been using CGM consistently (>5 days/week) for at least the past 6 months. Once identified in clinic or once someone has expressed interest in the study, study staff will approach potential participants to explain the study, determine eligibility, and obtain informed consent. All participants will complete their baseline visit remotely. This baseline visit will include 1) completing a hemoglobin A1c test kit that is mailed to them in advance; 2) completing a baseline assessment survey online via a secure site (REDCap) to obtain demographic and psychosocial data and 3) initiate use of CGM supplies. Participants will be given the choice of using Dexcom G6 or Libre 2 CGM. Participants will be mailed 12 weeks of CGM supplies of their choice and will receive initial standard CGM introduction and education from the study staff and will be provided with standard resources from the device manufacturer at this baseline visit. At baseline, participants will then be randomized. We will randomize at a 1:1 ratio, intervention to control. Those randomized to the intervention (ONBOARD) condition will schedule 4 60-minute sessions with study interventionist (every 2 weeks), with the first session scheduled for 2 weeks after CGM initiation. Sessions will be conducted via a secure, HIPAA-compliant, videoconferencing software (Zoom) and may be recorded to ensure consistency and quality of the intervention across participants and interventionists. Each participant will receive one unique Zoom link that they will use for all 4 of their study sessions. At the 3-, 6-, and 12-month time points, participants will be mailed A1c test kits for follow-up A1cs, and will complete a follow-up REDCap survey at these time points as well. The follow-up survey will assess psychosocial variables, technology satisfaction, and changes to demographic/medical information. Each follow-up survey is expected to take 30 minutes to complete. Of note, all study participants will

receive instruction on how to work with their insurance to obtain coverage for continuing to use CGM after the first 12 weeks of the study. At the 3-, 6-, and 12-month timepoints, CGM data downloads will be obtained.

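### The covariates of the primary A1c model are left to criterion-guided selection and baseline A1c is not named; a fixed model with baseline A1c gains power for one parameter

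*Combined protocol and SAP*

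**What the plan says.** Section 2.7 of the combined protocol and SAP states the core of the A1c model: "we will use linear mixed models to model changes in A1c as a function of time, intervention assignment, and group-by-time interaction". A random effect per subject handles the repeated measurements, and the outcome is a change score: "We will examine change from baseline for each outcome as the dependent variable".

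The covariates are handled differently: "We will begin by fitting models with minimum covariates prior to considering additional covariates". None is named. After a sentence extending similar models to the secondary outcomes comes "We will reference information criteria (e.g., Akaike's) to inform model selection decisions". The next sentence is "Beyond testing the groups-by-time interaction term, custom contrasts will assess group differences at each time point". Exploratory analyses are introduced only after that, so the selection sentence is not confined to them.

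Baseline A1c is available for this purpose. Section 2.2 has every participant complete a mailed A1c kit at the baseline visit, at which randomization follows, and Table 4 in section 2.5 marks A1c at month 0. The CGM system is also a baseline choice: "Participants will be given the choice of using Dexcom G6 or Libre 2 CGM".

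**The concern.** The model that gives the primary A1c result should be known before anyone sees outcomes by arm. Here the covariate set is to be settled after a first fit, with arm in the model, by criteria whose scope is not given. They could govern covariates, covariance structure, the form of time or the interaction. No sentence says which fitted model is confirmatory.

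Two things could be at stake. The first is type I error, because p-values from a selected model ignore the selection. The second is precision, because the strongest baseline predictor of follow-up A1c is likely to be baseline A1c, and the plan does not commit to using it. The multiplicity rule does not help with the first: "We will adjust for multiple comparisons by using the Benjamini-Hochberg procedure and a false discovery rate of 0.05" deals with several comparisons, not with a choice among models for one comparison.

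**Working it through.** **Inputs from section 2.7.** α = .05 (two-sided assumed), d = .35, correlation .50, 89 per arm randomized, 76 per arm after 15% attrition, follow-up at 3, 6 and 12 months. Assumed in addition: complete data, and the same correlation ρ between any two visits.

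**1. The plan's own power figure.** With A1c variance set to 1, the average of three follow-up values has variance (1+2ρ)/3 = 2/3 = 0.667. The average change from baseline has variance 0.667 + 1 − 2ρ = 0.667. At ρ = .50 the two are equal, so subtracting baseline gains nothing. Power is Φ(d·√(n/2)/√V − 1.96).

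- 89 per arm: .35·√44.5 = 2.335; 2.335/√0.667 = 2.860; power .816. The plan's claim of power above 0.80 reproduces.
- 76 per arm: .35·√38 = 2.158; 2.158/√0.667 = 2.642; power .753.

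**2. With baseline A1c in the model.** For the averaged effect, V = 0.667 − ρ² = 0.667 − 0.25 = 0.417. For a single visit, V falls from 2(1−ρ) = 1 to 1 − ρ² = 0.75.

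| Effect tested, d = .35 | Per arm | Change score only | With baseline A1c |
|---|---|---|---|
| Average of 3, 6, 12 months | 76 | .753 | .917 |
| Average of 3, 6, 12 months | 89 | .816 | .951 |
| Single visit | 76 | .578 | .702 |
| Single visit | 89 | .646 | .769 |

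The gain depends on ρ. For the averaged effect the variance ratio is 0.417/0.667 = 0.625 at ρ = .50. At an assumed ρ = .70, average change has variance 0.80 + 1 − 1.40 = 0.40 and the adjusted value is 0.80 − 0.49 = 0.31, a ratio of 0.775. The gain shrinks but stays.

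**3. Type I error from selecting covariates only.** These are simulations under the null with 76 per arm, always keeping arm. The number of candidates is assumed, since the plan gives none.

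- 5 candidates, best subset by Akaike's criterion, 8,000 trials: 5.3 to 5.5%, against 5.1 to 5.3% for fixed models in the same runs.
- 5 candidates, forward selection, 30,000 trials: 4.9% becomes 5.3%.
- 12 candidates, forward selection, 30,000 trials: 5.0% becomes 5.8%.
- 12 candidates, 3 of them weakly prognostic, 4,000 trials: 5.3% becomes 6.25% (simulation error about 0.4 points).

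The inflation is thus about 0.3 to 1 percentage point.

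**4. Type I error if the criterion also chose time or interaction terms.** These rules are hypothetical. Akaike's criterion keeps a 2-df interaction when its likelihood-ratio statistic exceeds 4. Under the null this has probability exp(−2) = .135 (simulated 13.8%).

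- Interaction tested if kept, otherwise the average effect: every 5% rejection of the interaction exceeds the threshold of 4, so the error is .05 + (1 − .135)(.05) = 9.3% (simulated 9.35%, 200,000 trials).
- 3-month contrast if kept, otherwise the average effect: 6.0%.
- Criterion picks linear or categorical time, then the interaction is tested: 7.2%.
- One fixed model and one named test: 5.0%.

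**The case against.** The strongest reply is that the plan already fixes what matters. Time, arm, their interaction, a subject random effect and the change-score outcome are all named. The sentence after the one on information criteria speaks of testing the interaction and giving contrasts at each visit, which implies that the interaction stays. Information criteria are ordinary practice for choosing a covariance structure, and that may be all that is meant. Adding baseline covariates to a linear model in a randomized trial does not change the effect being estimated.

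Most of this stands, and it excludes three stronger readings.

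- A reader might infer that Akaike's criterion will choose the model's main terms, and so decide whether a visit-specific or an averaged A1c effect is tested. The text does not say so. The 6 to 9% error rates belong to rules that the plan does not state.
- A reader might infer that the 5% level is materially lost in any case. Covariate selection alone does not do that. Picking the smallest p-value across models would do more, but the plan names information criteria, not p-values.
- A reader might want to make the 3-month contrast the deciding test as part of the same correction and call it free. It is not. Section 2.7 powers a repeated-measures comparison over 3, 6 and 12 months. Even with baseline A1c, a single visit at d = .35 reaches only .70 with 76 per arm and .77 with 89.

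The reply does not cover the covariates. None is named, the selection sentence has no stated scope, and a change score does not replace a baseline term.

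**Conclusion.** The point holds as a gap in prespecification with a measurable cost in precision. The confirmatory A1c model has no fixed covariate set and no commitment to baseline A1c, and an unscoped sentence lets outcome-based criteria guide the choice. Under the working's assumptions, committing to baseline A1c takes the averaged comparison with the expected completers from below the plan's 0.80 target to well above it. The error-rate part is minor for covariates. It becomes material only under uses of the criterion that the plan leaves open without stating.

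A case for adjusting for CGM device is weaker. If device explained 2 to 10% of time-in-range variance (an assumed range), the gain would be 152·(1/(1−R²) − 1), or about 3 to 17 participants. That concerns a secondary outcome, not A1c.

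Uncertainty over which A1c effect decides has another source. Sections 1.1 and 2.1 stress the comparison over the first 3 months, while section 2.7 models and powers 3, 6 and 12 months and names no deciding contrast. That needs its own reconciliation.

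**What to change.** In section 2.7, state the confirmatory model as arm, visit (categorical), arm-by-visit and the baseline value of the outcome, with the subject random effect, all kept whatever their fit. For CGM-derived outcomes, the device chosen at baseline may be added as a fixed term. The baseline value for those outcomes needs defining, because Table 4 marks CGM measures at month 0 while section 2.2 lists downloads at 3, 6 and 12 months only.

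Limit information criteria to the covariance structure and to exploratory or sensitivity models, and label any further-adjusted A1c model as a sensitivity analysis. Settle this before outcomes are examined by arm. Leave the choice of deciding contrast to its own amendment, so that it does not change as a side effect.

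The cost is a few sentences in the SAP and one model parameter for baseline A1c (one more where device is included). No participants, visits or A1c measurements are added.

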1.1. Purpose

The primary objective of this randomized controlled trial is to examine the impact of a behavioral support intervention for adults with type 1 diabetes (T1D) who are starting on continuous glucose monitoring (CGM). This trial compares adults with T1D who are starting on CGM with behavioral supports (the intervention group) versus those who are starting on CGM without behavioral supports (the control group). We will examine group differences over a 3-month period on two sets of outcomes. The first set of outcomes includes glycemic variables (e.g. hemoglobin A1c, time in range). In this set of outcomes, A1c is the identified primary endpoint. The second set of outcomes includes psychosocial variables (e.g. diabetes distress, worry about hypoglycemia, technology attitudes), with diabetes distress as the primary endpoint. After the initial comparison of intervention to control across the first 3 months after starting CGM, we will conduct a longitudinal follow-up of glycemic and psychosocial outcomes at 6 and 12 months.

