2.3. Study groups

There are two groups in this study: intervention (ONBOARD) and control (CGM-only). All participants will receive 12 weeks of CGM supplies and will receive standardized education about getting started with CGM. A person trained in delivering education about CGM will deliver education about CGM use and will be present during a virtual meeting while participant is inserting first sensor during training. This individual will be available to assist with questions from participants. In addition, Dexcom and Abbott representatives are available to participants for technical questions or issues with the system, just like the access any CGM user has. All participants in both groups will be required to actively use CGM for 12 weeks. After that time period, they can continue or discontinue use of CGM. If they decide to continue, the study team will provide information on working with insurance and with their provider to obtain CGM for both study groups.

After randomization, participants in the intervention group will receive 4 one-on-one sessions of ONBOARD (OvercomiNg Barriers & Obstacles to Adopting Diabetes Devices). Sessions will be held every 2-3 weeks over the 12-week period

when participants are using CGM provided by the study. ONBOARD is a multicomponent intervention to provide tailored support for CGM adoption. Session content and strategies are outlined in Table 3. Sessions target four primary topics. Each participant will receive content in the same order, but the program is designed to be flexible depending on individual barriers and concerns. Some participants may spend more time on certain topics than others. ONBOARD will approach CGM data interpretation

Table 3. ONBOARD Intervention Topic Content			
Barrier addressed	Topic name	Strategies used	Goals
	Introduction	- Psychoeducation; rapport building	
 - Provide rationale for ONBOARD - Introduce concepts from Technology Acceptance Model to discuss CGM pros and cons
Physical	Wearing Diabetes Device(s)	- Experiential wear	
 - Troubleshooting device placement - Provide education and examples of problem solving for common concerns and strategies for navigating them: appearance, insertion, skin irritation, discomfort, interference with daily activities - Provide resources for adhesive, skin prep, and adhesive removal

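### Section 2.7 never names the A1c test that decides the primary hypothesis, and its analysis over 3, 6 and 12 months does not match the 3-month comparison in 1.1 and 2.1

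*Combined protocol and SAP*

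**What the plan says.** Sections 1.1 and 2.1 set the group comparison over a 3-month period and name A1c the primary endpoint of the glycemic set. They place the later visits after it: "After the initial comparison of intervention to control across the first 3 months after starting CGM, we will conduct a longitudinal follow-up" at 6 and 12 months.

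Section 2.7 tests Hypotheses 1 and 2 by a "treatment group comparison (ONBOARD vs. CGM-only) of the change in A1c, the primary outcome, from baseline to 3, 6, and 12 months". The linear mixed model has terms for time, arm and their interaction, and a random subject effect. On the outcome, 2.7 says: "We will examine change from baseline for each outcome as the dependent variable". On tests, it says: "Beyond testing the groups-by-time interaction term, custom contrasts will assess group differences at each time point". On covariates: "We will begin by fitting models with minimum covariates prior to considering additional covariates".

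The sample-size paragraph of 2.7 uses a repeated measures ANOVA on change over the same three visits, with alpha 0.05 and autocorrelation 0.50. It states power above 0.80 for d = 0.35 with 89 per arm, and expects 76 per arm after 15% attrition. It attributes the expected A1c difference partly to more sustained CGM use over 12 months and partly to added benefit from use.

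**The concern.** A reader of 1.1 and 2.1 would take the 3-month A1c difference as the question the trial answers first. A reader of 2.7 would take an effect across 3, 6 and 12 months. No sentence ranks one above the other or says which result settles the hypothesis. If that is left open until the data are seen, the choice can follow the result.

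The interaction makes this worse, because 2.7 mentions it first among the tests. In a model for raw A1c with baseline as one of the time levels, a group-by-time term would carry the treatment effect. Here baseline has already been subtracted and only post-baseline visits remain, so the term carries only the change in the arm difference between visits.

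The two remaining readings could diverge under the plan's own rationale. Section 2.3 says: "All participants in both groups will be required to actively use CGM for 12 weeks". The part of the effect that comes from sustained use would therefore show mostly after 3 months.

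**Working it through.** **Inputs from section 2.7.** d = 0.35; correlation 0.50; alpha 0.05; 89 per arm randomised; 89 × 0.85 = 75.65, so 76 per arm expected; 0.5% as the minimum clinically significant A1c difference; SD 1.2, or nearer 1.0.

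**Assumptions added here.** Two-sided test (sidedness is not stated); raw A1c variance set to 1; compound symmetry (CS) unless stated. Power is from the noncentral t with 2n − 2 degrees of freedom and noncentrality d / √(2v/n), where v is the variance of the quantity compared.

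**Variances under CS, correlation 0.50**
- Averaged change: mean of three visits (1 + 2 × 0.5)/3 = 0.667; less baseline, 0.667 + 1 − 2 × 0.5 = 0.667.
- 3-month change: 1 + 1 − 2 × 0.5 = 1.
- With baseline A1c as covariate: averaged 0.667 − 0.5² = 0.417; 3-month 1 − 0.5² = 0.75.

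**The plan's own figure.** Averaged effect, 89 per arm: 0.35 / √(2 × 0.667/89) = 2.86, power 0.812. The stated power above 0.80 reproduces. At 76 per arm: 0.35 / √(2 × 0.667/76) = 2.64, power 0.747.

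**Power at d = 0.35**

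| Test | v | 76 per arm | 89 per arm | Evaluable n per arm for 0.80 |
|---|---|---|---|---|
| Averaged, unadjusted, CS | 0.667 | 0.747 | 0.812 | 87 |
| Averaged, baseline covariate, CS | 0.417 | 0.913 | 0.949 | 55 |
| 3-month, unadjusted | 1 | 0.573 | 0.641 | 130 |
| 3-month, baseline covariate | 0.75 | 0.697 | 0.765 | 98 |
| Averaged, unadjusted, AR(1) | 1.028 | 0.561 | 0.629 | 133 |
| Averaged, baseline covariate, AR(1) | 0.526 | 0.840 | 0.893 | 69 |

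The AR(1) rows cover the possibility that autocorrelation means first-order decay by visit. Correlations with baseline are then 0.5, 0.25 and 0.125 (mean 0.2917), and those among the later visits 0.5, 0.5 and 0.25. The variance of the mean is (3 + 2 × 1.25)/9 = 0.611. The averaged change has 0.611 + 1 − 2 × 0.2917 = 1.028, and with the covariate 0.611 − 0.2917² = 0.526. The 3-month rows do not depend on this choice.

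**Power for a 0.5% difference, 3-month contrast, unadjusted.** SD 1.2 (d = 0.5/1.2 = 0.417): 0.723 to 0.789. SD 1.0 (d = 0.50): 0.865 to 0.913.

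**Interaction.** If the arm differences are 0.35, 0.35 and 0.35, both between-visit differences are 0. The noncentrality is then 0 and power equals alpha, 0.05.

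**Disagreement between the 3-month and averaged tests (simulation, 40,000 runs per cell, CS, unadjusted).** For a constant 0.35, one is significant and the other not in 0.227 of trials at 76 per arm and 0.213 at 89. Under a growing effect of 0.20/0.35/0.50 the figures are 0.518 and 0.552. That profile is an illustration chosen for this review and is not in the documents.

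**The case against.** The strongest reply is that 2.7 is the operative section and is consistent within itself. It compares the arms on A1c change over three visits and powers that same comparison, while 1.1 and 2.1 never use the term primary time point and may only describe the order of reporting. This stands in part: the averaged effect is the likely reading, and the plan is not missing an analysis. But 2.7 does not list it among the tests it names, and 1.1 and 2.1 call the 3-month comparison the initial one.

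Stronger readings that a reader might infer, and that the documents do not support:
- *The 3-month test is underpowered in general.* That follows from d = 0.35. For 0.5% at the SD of 1.0 that 2.7 thinks more likely, the unadjusted contrast exceeds 0.80 at both sample sizes.
- *The stated power fails after attrition.* The figure for 76 per arm is a floor. Section 2.7 starts from a missing-at-random analysis and 4.4 keeps data up to withdrawal, so partial follow-up counts. If, as an assumption, 85/80/76 or 89/82/76 per arm are seen at 3, 6 and 12 months, averaged power is about 0.79 or 0.80.
- *The two tests would give opposite answers, usually.* They differ in significance, not in direction, and the figure above one half rests on the illustrative growing profile. The rationale also names added benefit from use, which can act within 12 weeks.
- *The false-positive rate is badly inflated.* The chance of any p < 0.05 among five A1c tests (three contrasts, interaction, average) is about 0.16 with no adjustment, but 2.7 specifies Benjamini-Hochberg. Applied to all five, it gives about 0.04. The correction still cannot say which test is primary.

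**Conclusion.** The point holds as a conflict over timing between 1.1/2.1 and 2.7, together with the absence of a named deciding test. It is not a missing analysis. The stated power belongs to the averaged effect at 89 per arm under compound symmetry and does not carry over to the 3-month contrast at d = 0.35, which is below 0.80 throughout the 76 to 89 range. Even with a constant effect, the choice between the two supportable tests changes the significance verdict in roughly one trial in five. The interaction should not decide efficacy under any reading of 2.7 as written.

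The averaged test's advantage depends on the correlation structure: under AR(1) and without the covariate it has no more power than the 3-month test. All figures rest on the two-sided level and the plan's correlation of 0.50.

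**What to change.** Before outcome data are examined by arm, name one primary A1c test in 2.7 and make 1.1, 2.1 and 2.7 agree. Either choice is open to the sponsor:

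- **Arm difference in A1c change averaged over 3, 6 and 12 months.** This matches the power basis; 1.1 and 2.1 must be amended. It moves the primary question away from 3 months and loses power if the benefit fades. For example, under an assumed 0.35/0.25/0.15 (mean 0.25) power is 0.47 to 0.53, or 0.66 to 0.73 with the covariate, under compound symmetry.
- **Arm difference at 3 months.** This matches 1.1 and 2.1; the claim of power above 0.80 at d = 0.35 must be restated, and is less favourable even with the covariate (0.70 to 0.76).

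Under either choice, use the interaction only to describe durability. Prespecify baseline A1c as a covariate in the primary model instead of leaving it to later model building. Restate power for the named test at the expected evaluable number, with the correlation structure stated.

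The cost is text. The planned model already yields both estimates and baseline A1c is already collected. With the covariate, the averaged test needs 55 evaluable per arm (compound symmetry) or 69 (AR(1)), both below the 76 expected. Without it, the needs are 87 and 133.

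Two smaller edits belong in the same amendment. List the tests in the Benjamini-Hochberg family. Give diabetes distress one status: 2.1 describes the psychosocial set "with diabetes distress as the primary endpoint", as does 1.1, but 2.7 says "Similar models will be used to examine secondary outcomes of time in range, days of CGM wear (Hypothesis 1), diabetes distress".
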